## 1.0 PROTOCOL SUMMARY AND/OR SCHEMA

[figure not shown]
This is a randomized phase II study entitled “A Phase II Randomized Trial of Intralesional Talimogene Laherparepvec with or without Hypofractionated Radiotherapy for Cutaneous Melanoma or Merkel Cell Carcinoma, or Other Solid Tumors.” Patients with cutaneous metastases from melanoma, Merkel cell carcinoma, and other solid tumor malignancies will be studied. Patients must have at least one cutaneous metastasis amenable to intralesional oncolytic immunotherapy with Talimogene Laherparepvec and radiotherapy and one metastasis amenable to observation.

The primary objective of the study is to characterize the systemic response of metastases not injected or irradiated in patients treated with Talimogene Laherparepvec with or without radiotherapy.

The secondary objectives of the study are to characterize the clinical efficacy, safety, patient reported quality of life, duration of response, time to response onset, progression free and overall survival associated with the treatment of patients with Talimogene Laherparepvec with or without radiotherapy.

The exploratory objective of the study is to characterize the immunologic response associated with the treatment of patients with Talimogene Laherparepvec with or without radiotherapy.

It is estimated that a minimum of 18 and a maximum of 34 patients will be enrolled over a minimum of 2 and a maximum of 3 years to complete the study over a minimum of 3 and a maximum of 4-year time period.

## 2.0 OBJECTIVES AND SCIENTIFIC AIMS

### Primary Objectives:

1. To assess the systemic efficacy of Talimogene Laherparepvec with or without radiotherapy in patients with cutaneous metastases from melanoma, Merkel cell

carcinoma, or other solid tumor malignancy. Systemic efficacy will be measured by the subject level modified WHO (mWHO) defined response of a metastasis not injected with Talimogene Laherparepvec or irradiated 16 weeks after initiation of therapy. A systemic response rate of  $\leq 7.5\%$  is unacceptable and a rate of  $\geq 27\%$  is acceptable (for both arms).

**Secondary Objectives:**

1. To assess the clinical efficacy of Talimogene Laherparepvec with or without radiotherapy in patients with cutaneous metastases from melanoma, Merkel cell carcinoma, or other solid tumor malignancy. Clinical efficacy will be measured by determining the objective response rate (ORR) defined as patients achieving complete response or partial response defined by the modified World Health Organization (mWHO) criteria. Response will be assessed approximately 16 weeks after the first treatment. Among patients randomized to receive Talimogene Laherparepvec, we expect ORRs to be comparable to previous studies (26.4% 95% CI 21.4-31.5%). Patients randomized to receive Talimogene Laherparepvec and radiotherapy are expected to have ORRs higher than previously published studies of Talimogene Laherparepvec alone.
2. To assess the safety of Talimogene Laherparepvec with or without radiotherapy in patients with cutaneous metastases from melanoma, Merkel cell carcinoma, or other solid tumor malignancy as measured by the frequency of adverse events (grade 2-5 adverse events). The window for adverse event assessment will include the 20 week time period from first treatment until 5 weeks after last treatment. We expect that frequency and grade of adverse events in patients receiving Talimogene Laherparepvec will be similar to previous studies of Talimogene Laherparepvec alone, and that radiotherapy will increase the frequency and grade of adverse events.
3. To evaluate the patient reported quality of life following Talimogene Laherparepvec with or without radiotherapy in patients with cutaneous metastases from melanoma, Merkel cell carcinoma, or other solid tumor malignancies treated with Talimogene Laherparepvec with or without hypofractionated radiotherapy. It is expected that quality of life (described further in section 12.0) will improve after Talimogene Laherparepvec with or without radiotherapy.
4. To assess the duration of response (DOR) in patients achieving a partial or complete response. DOR will be defined as the duration of time from occurrence of partial or complete response until first occurrence of progression or date of death if the patient dies due to any causes before progression.
5. To assess the time to response onset in following Talimogene Laherparepvec with or without radiotherapy. It is expected that the time to response onset in patients randomized to receive Talimogene Laherparepvec will be similar to previous studies of Talimogene Laherparepvec alone (median 4.1 months, range 1.2-16.9 months). It is anticipated that the time to response onset in patients receiving Talimogene Laherparepvec and radiotherapy will be earlier than prior studies of Talimogene Laherparepvec alone.

6. To estimate progression free and overall survival in patients receiving Talimogene Laherparepvec with or without radiotherapy for cutaneous metastases from melanoma and Merkel cell carcinoma. Progression free survival will be defined as the time elapsed from start of protocol treatment until progression (according to mWHO criteria) or death.

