### 4.2 Intervention

Patients with cutaneous metastases from melanoma, Merkel cell carcinoma or other solid tumor malignancy will be screened for eligibility. If a patient is found to have anything other than cutaneous metastases from melanoma, Merkel cell carcinoma or other solid tumor malignancy, appropriate clinical management will be undertaken.

If eligible, patients will undergo baseline PET/CT imaging, quality of life assessment, followed by intralesional Talimogene Laherparepvec with or without radiotherapy.

Talimogene Laherparepvec will be administered at weeks 0, 3, 5, 7, 9, 11, 13 and 15. The first dose of Talimogene Laherparepvec will be  $10^6$  plaque forming units (PFU)/mL, followed three weeks later by a dose of  $10^8$  pfu/mL. Up to 4 mL will be injected at each treatment. Metastases will be injected, beginning with the largest tumor first, with volumes indicated below, until a maximum of 4 mL has been used.

Tumor size (longest dimension)	Talimogene Laherparepvec (TVEC) injection volume	Dose concentration
>5 cm	$\leq 4$ mL	$10^6$ PFU/mL at week 0, $10^8$ PFU/mL thereafter
2.6-5 cm	$\leq 2$ mL	$10^6$ PFU/mL at week 0, $10^8$ PFU/mL thereafter
1.6-2.5 cm	$\leq 1$ mL	$10^6$ PFU/mL at week 0, $10^8$ PFU/mL thereafter
0.6-1.5 cm	$\leq 0.5$ mL	$10^6$ PFU/mL at week 0, $10^8$ PFU/mL thereafter
$\leq 0.5$ cm	$\leq 0.1$ mL	$10^6$ PFU/mL at week 0, $10^8$ PFU/mL thereafter

Table 1. TALIMOGENE LAHERPAREPVEC injection volume and concentration based on tumor size.

Patients randomized to Arm A will receive 3 radiotherapy treatments (one treatment every 3-6 days) during weeks 3 and 4. The first treatment will occur 6 (+/- 2) hours after the Talimogene Laherparepvec administration at week 3.

Patients randomized to Arm B will receive Talimogene Laherparepvec alone, as described above, without radiotherapy.

Patients will undergo disease re-evaluation with PET/CT and quality of life assessment at week 16.

Patients with potential for clinical benefit may continue Talimogene Laherparepvec every 2 weeks, after week 15, for up to 24 weeks. This will be determined by the treating clinician.

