## 10.0 EVALUATION DURING TREATMENT/INTERVENTION

Study Timeline	Pre-Treatment	Treatment									End of Treatment 	Follow-Up 
		0 (1)	3 (1)	5 (1)	7 (1) 	9 (1)	11 (1)	13 (1)	15 (1)	16 (1)		
Week (+/-)	-4 to 0											
Assessments												
Pathology Review	X											
PET/CT (with or without contrast)	X									X		
Quality of life questionnaires	X									X		
Digital photography	X									X		
Adverse event		X	X	X	X	X	X	X	X	X		X

review 											
ECOG performance status	X	X	X	X	X		X		X	X	
Vital signs (weight, heart rate, blood pressure, respiratory rate, oxygen saturation)	X	X	X	X	X		X		X	X	
Physical exam	X	X	X	X	X		X		X	X	
Complete medical history	X										
Hepatitis B Surface Antigen, Hepatitis B Core Antibody (total), hepatitis B surface Antibody, Hepatitis C Antibody 	X										
Comprehensive metabolic profile	X									X	
Basic metabolic profile		X	X	X	X		X		X		
Complete blood count	X	X	X	X	X		X		X		
PT&APTT	X	X	X	X	X		X		X		
Pregnancy testing (blood or urine); WOCBP only	X 		X		X		X		X		
Research blood test 		X	X	X	X		X		X		
Research skin punch biopsy 		X			X				X		
Treatment											
TALIMOGENE LAHERPAREPVEC		X	X	X	X	X	X	X	X†		
Radiation therapy			X*								

†Patients with potential for clinical benefit may continue TALIMOGENE LAHERPAREPVEC after week 15 every 2 weeks for up to 24 weeks (as determined by treating clinician)

\*Only for Arm A; first fraction given 6 (+/- 2) hours after week 3 TALIMOGENE LAHERPAREPVEC administration; 2nd and 3rd fraction given every 3-6 days over no more than 14 days

Including Appendix C, "NCI PRO-CTCAE v1.0"

Within 2 weeks of starting Talimogene Laherparepvec treatment

 Research bloods will be 3 tubes (3 CPT) at each time point; stored at immune monitoring core facility for up to 1 year after completion of study

One lavender top (EDTA) tube of blood will be drawn on the same day as the research skin punch biopsy; window for biopsy will be +/- 3 weeks

Additional testing to evaluate for hepatitis maybe required depending on the serological results

For patients that discontinue TVEC before week 16, the End of Treatment visit occurs after last dose of TVEC

Follow-Up at week 20 or 4 weeks after last TVEC dose

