#### 11.1.3.1 Definitions of Dose Limiting Toxicity

Toxicity should be evaluated according to CTCAE version 4.0, and should only include events assessed as related to talimogene laherparepvec during treatment and up to 30 days after the last talimogene laherparepvec injection.

The following herpetic events should be considered as DLTs:

- Serious herpetic events such as herpetic encephalitis, encephalomyelitis or disseminated herpetic infection
- Any herpetic events confirmed due to talimogene laherparepvec that require treatment with acyclovir or similar anti-viral agent. Talimogene laherparepvec treatment should be suspended if treatment is required with systemic acyclovir or other anti-virals. If ongoing anti-viral treatment is required, talimogene laherparepvec treatment should be permanently discontinued

Consider also including the following as DLTs:

- Grade 3 or greater immune-mediated adverse events
- Any grade plasmacytoma at or near the injection site or evidence of impaired wound healing at the injection site
- Grade 3 or greater allergic reactions considered at least possibly related to talimogene laherparepvec
- Grade 4 non-hematologic toxicity
- Grade 3 non-hematologic toxicity lasting > 3 days despite optimal supportive care
  - Grade 3 fatigue will not be classified as DLT, irrespective of duration
- Any grade 3 or higher non-hematologic laboratory value if the abnormality:
  - fails to respond to medical intervention, or
  - leads to hospitalization, or
  - persists for > 1 week unless deemed not clinically important per both investigator and sponsor
- Grade 3 or 4 febrile neutropenia
- Grade 4 thrombocytopenia associated with a bleeding event deemed at least possibly related to talimogene laherparepvec and requiring intervention
- Any other intolerable toxicity leading to permanent discontinuation of talimogene laherparepvec
- Grade 5 toxicity (ie. Death)

If an unexpected DLT deemed at least possibly related to talimogene laherparepvec occurs, talimogene laherparepvec administration should be delayed until the DLT has resolved to at least CTCAE (v. 4.0) Grade 1.

If talimogene laherparepvec dosing is delayed by more than 6 weeks from the date of the planned dose due to the occurrence of an adverse event that is considered related to talimogene laherparepvec, the subject must be permanently taken off talimogene laherparepvec treatment.

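### The adverse-event window is consistent only if the last dose is at week 15, and the arms are compared without a common window

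*Combined protocol and SAP*

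**What the plan says.** The safety endpoint (Section 2.0, Secondary Objective 2) is the frequency of grade 2-5 adverse events. Its period is defined in one sentence: "The window for adverse event assessment will include the 20 week time period from first treatment until 5 weeks after last treatment".

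Section 4.2 gives the core schedule: "Talimogene Laherparepvec will be administered at weeks 0, 3, 5, 7, 9, 11, 13 and 15". It adds that patients thought able to benefit "may continue Talimogene Laherparepvec every 2 weeks, after week 15, for up to 24 weeks". On who decides, it says: "This will be determined by the treating clinician".

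The last adverse-event review is set in Section 9.0 (Follow-Up) and in footnote 7 of Section 10.0: "Follow-Up at week 20 or 4 weeks after last TVEC dose". No rule says which of the two applies. Section 9.0 lists adverse-event review for weeks 0 to 15, at week 16 and at follow-up. The Section 10.0 table has no review column between week 16 and follow-up. Section 9.1 asks for toxicity evaluation every 2-3 weeks while the drug is given, but refers to Section 10.0 for the timing.

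Section 14.0 handles safety in the same way as ORR: a sample proportion per arm and a comparison between arms. It states no common window and no adjustment for exposure.

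Two 30-day periods also appear. Section 11.1.3.1 limits dose-limiting toxicities to related events "during treatment and up to 30 days after the last talimogene laherparepvec injection". Section 17.2 requires SAE reporting for 30 days, and keeps later events reportable if they are at least possibly related.

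**The concern.** The endpoint window has two anchors, first treatment and last treatment. They define the same period for only one dosing history. For any other history the plan does not say which anchor governs, and the permitted final review need not reach the end of the window under either.

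What is at stake is the between-arm safety comparison, where the plan expects radiotherapy to raise the frequency and grade of events. A proportion with at least one event grows with time observed. If time observed depends on how long a patient is dosed, and dosing differs by arm, part of any difference in proportions reflects observation time rather than treatment. The decision to continue rests with the treating clinician, and Section 12.0 blinds only the study radiologists.

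**Working it through.** **1. The plan's own figure.** Last core dose at week 15, plus 5 weeks, is week 20. The stated 20 weeks reproduces, and the week 20 visit closes the window. Section 9.0 allows ±1 week on both the dose and the visit, so that visit can fall 3 weeks (19 − 16) to 7 weeks (21 − 14) after the last dose.

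**2. Other dosing histories.** For a last T-VEC dose at week w, the 5-week window ends at w + 5 and the alternative final review falls at w + 4. The 24-week limit can mean study week 24 (doses at weeks 17, 19, 21 and 23) or 24 further weeks (doses at weeks 17 to 39).

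| History | Last dose | 5-week end | Review at 4 weeks | Fixed end |
|---|---|---|---|---|
| Stops after week 3 | 3 | 8 | 7 | 20 |
| Stops after week 13 | 13 | 18 | 17 | 20 |
| Core schedule | 15 | 20 | 19 | 20 |
| Continues, limit is study week 24 | 23 | 28 | 27 | 20 |
| Continues, 24 further weeks | 39 | 44 | 43 | 20 |

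- A review at 4 weeks is always 35 − 28 = 7 days short of the 5-week end.
- For an early stopper it is also short of week 20: by 3 weeks after a last dose at week 13, and by 13 weeks after a last dose at week 3.
- For a patient who continues, the 5-week window is 28/20 = 1.4 or 44/20 = 2.2 times the fixed one.

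**3. Anchor wording.** Section 2.0 counts from last treatment, while Sections 9.0 and 10.0 count from the last T-VEC dose. These can differ in Arm A. Suppose T-VEC stops after week 3 and radiotherapy is still completed, using the 14-day limit in Sections 9.0 and 10.0. Treatment then ends as late as week 5 and the 5-week window ends at week 10, but the 4-week review is at week 7.

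**4. Illustration of size.** The documents give none of the inputs in this step. Assume a constant hazard, the same in both arms, and risk p of at least one grade 2-5 event by week 20. The risk by week t is 1 − (1 − p)^(t/20). Assume also that 50% of Arm A and 20% of Arm B continue, that each is followed to the full 5-week end, and that all others are followed to week 20. The gap between arms is then (0.50 − 0.20) × (risk by t − p).

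| p by week 20 | Risk by week 28 | Gap, points | Risk by week 44 | Gap, points |
|---|---|---|---|---|
| 10% | 13.7% | 1.1 | 20.7% | 3.2 |
| 30% | 39.3% | 2.8 | 54.4% | 7.3 |
| 50% | 62.1% | 3.6 | 78.2% | 8.5 |
| 70% | 81.5% | 3.4 | 92.9% | 6.9 |

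For p = 30% and week 44, the arm proportions are 0.30 + 0.50 × 0.244 = 42.2% and 0.30 + 0.20 × 0.244 = 34.9%. If the same share continues in both arms, every gap is 0. If Arm B continues more often, the sign reverses.

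**5. Scale.** With 15 evaluable patients per arm, 7.3 points is 0.073 × 15 = 1.1 patients. The standard error of 42% against 35% is √(0.42 × 0.58/15 + 0.35 × 0.65/15) = 0.18, or about 18 points.

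**The case against.** The strongest reply is that Section 2.0 names a 20-week period from first treatment. If that governs, both arms share one window and extension adds nothing. This answers the point for patients who continue, but not for those who stop early: a patient reviewed for the last time 4 weeks after the last dose is not observed to week 20. The sentence also carries the 5-week clause, and nothing ranks one over the other.

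It is also fair to say that the illustration rests on assumed inputs. A constant hazard is doubtful in Arm A, where radiotherapy falls in weeks 3 and 4 and Section 11.2 lists grade 2 radiation dermatitis at 50%. Any distortion is small beside the sampling error at this sample size. All of that stands, and it is why the size is left open.

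A reader might infer three stronger things that the documents do not support.

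- **That four rival follow-up periods are stated.** The 20 weeks counts from first treatment and matches the 5 weeks on the core schedule. The 30-day periods serve DLT classification and SAE reporting, so differing from the endpoint window is not a contradiction.
- **That the endpoint cannot be ascertained.** For a last dose at week 15 the week 20 visit closes the window, subject to visit allowances, and Section 9.1 provides for toxicity evaluation during dosing.
- **That Arm A will look more toxic because its responders are watched longer.** Continuation rests on the clinician's view of likely benefit, not on response as such. Under a window tied to the last dose, stopping early for toxicity shortens observation and pulls the other way.

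**Conclusion.** The inconsistency stands in a limited form. The endpoint window is coherent only for a last dose at week 15. For patients who continue, the two anchors differ by 8 or 24 weeks (28 − 20 or 44 − 20). For patients who stop early, the permitted final review ends before the window under either anchor. Because Section 14.0 sets no common window, the between-arm comparison is open to distortion if continuation or early stopping differs by arm. The documents do not show that it will differ, so neither direction nor size is established. The figures of about 3 and 7 points hold only for the assumed constant hazard, 30% risk and 50% against 20% continuing. This concerns a secondary endpoint, and the response-based primary analysis is untouched.

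**What to change.** - **Analysis (Section 14.0).** Define the between-arm safety comparison as grade 2-5 events from first dose to a common cut at week 20. State how patients whose review ends earlier are handled, for instance by time to first event or by reporting observed time beside the proportion.
- **Extension.** Report events after the cut separately, by arm, with exposure time.
- **Reconciliation by the sponsor.** Align Section 2.0 with the follow-up visit in Sections 9.0 and 10.0, so that the last adverse-event review does not precede the end of the endpoint window. Say which of the two visit timings applies to whom. State what the 24-week limit is counted from, and whether last treatment means the last T-VEC dose or also radiotherapy. The length of follow-up is the sponsor's decision.
- **No change needed** to the 30-day DLT and SAE periods. Forcing one figure on them would alter a DLT definition that governs stopping of treatment.

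The cost is wording and, for some patients, a later final review. This is one week later if the 5-week end is used. If week 20 is used it can be longer for early stoppers: 3 weeks after a last dose at week 13, and 13 weeks after a last dose at week 3.

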**Exploratory Objectives:**

1. To characterize the immunologic response to Talimogene Laherparepvec with or without radiotherapy in patients with cutaneous metastases from melanoma, Merkel cell carcinoma, or other solid malignancies. Tumor biopsies and peripheral blood specimens will be used to characterize immunologic effects of treatment such as tumor infiltrating lymphocytes and peripheral blood immunophenotype, serum antibody titers and cytokine array analyses.

[figure not shown]
### **3.0 BACKGROUND AND RATIONALE**

**Cutaneous metastases.** Secondary malignant neoplasms of the skin (also referred to as cutaneous metastases) are not infrequently encountered in patients with advanced cancer. According to one study, 5.3% of patients with solid tumors develop cutaneous metastases (Krathon RA South Med J 2003). Practically, the anatomic compartment of “cutaneous metastases” includes the skin (cutis) and superficial subcutaneous soft tissues and lymphatics (in-transit channels as well as lymph nodes). The disorder is especially common in high-risk skin malignancies, including melanoma and Merkel cell carcinoma. Cutaneous metastases can lead to problems such as infection, hemorrhage, and discomfort. One study demonstrated that the presence of cutaneous metastases was the single most deleterious factor in patient quality of life (Shimozuma K Surg Today 1995). Surgical excision may be a simple and effective means of dealing with cutaneous metastasis, but is not always possible because of patient comorbidities or extent of the cutaneous metastases. Systemic therapy alone often has limited efficacy for cutaneous metastases (Richtig E Br J Dermatol 2005). We have recently reported on the efficacy of a variety of skin-directed therapies (such as radiation therapy and intralesional therapy) for cutaneous metastases, and found that treatment is well-tolerated, associated with improvements in quality of life, and frequently leads to reduction in size of the treated tumor (Spratt DE J Clin Oncol 2014). The systemic efficacy of skin-directed therapy on non-treated metastases has not been well-characterized.

[figure not shown]
**Radiotherapy for cutaneous metastases.** Radiotherapy has been used for many years as a palliative treatment for cutaneous metastases. Our recent meta-analysis of skin-directed therapies for cutaneous metastases demonstrated that radiotherapy yields a complete response in 62.7% (95% CI 22.8-90.5%), and an objective response in 83.8% (95% CI 37.9-97.8%). Moreover, studies that combined radiotherapy with other skin-directed therapies (intralesional therapy or topical therapy) demonstrated even higher overall response rates (Spratt DE J Clin Oncol 2014). As noted above, the systemic efficacy to skin-directed radiotherapy has not been well-characterized. However, studies from our group and others have suggested that radiotherapy may augment immunologic response to produce systemic responses in non-irradiated metastases (Postow M N Engl J Med 2011, Barker CA Cancer Immunol Res 2013, Teulings H Br J Derm 2013).

**Talimogene laherparepvec (TALIMOGENE LAHERPAREPVEC) for cutaneous metastases.** Talimogene laherparepvec (TALIMOGENE LAHERPAREPVEC) is an intralesional oncolytic immunotherapy consisting of a modified type-1 herpes simplex virus that selectively replicates in malignant cells and stimulates an immune response. A phase I trial of Talimogene Laherparepvec (formerly OncoVEXGM-CSF) in 30 patients with cutaneous or subcutaneous metastases from a variety of malignancies (breast, head and neck, melanoma, gastrointestinal) who had failed prior therapy demonstrated the safety of this approach (Hu JC Clin Cancer Res 2006). A subsequent phase II study of 50 patients with cutaneous metastases from melanoma demonstrated an overall response rate of 26%, an revealed responses of metastases that were not injected (Senzer NN J Clin Oncol 2009). Correlative analyses suggested that response in metastases that were not injected were due to immunologic effects of Talimogene Laherparepvec (Kaufman HL Ann Surg Oncol 2010). Preliminary results of a phase III study of Talimogene Laherparepvec versus granulocyte monocyte colony stimulating factor (GM-CSF) for patients with unresectable stage IIIB-IV melanoma have been presented, and demonstrated an overall response rate of 26.4% (95% CI 2.7-29.2%), with a trend toward improved overall survival (Andtbacka RHI ASCO 2013). Responses were seen most often at the site of the injected cutaneous metastasis (64.3%), but also in non-injected cutaneous metastases (33.7%), and non-injected visceral metastases (15.2%). Importantly, the median time to response was 16 weeks, therefore approximately 7.5% of patients are expected to have response in uninjected metastases at this time point (Andtbacka RHI HemOnc Today Melanoma and Cutaneous Malignancies Meeting 2014). Increasing the response rate by combining Talimogene Laherparepvec with other therapies is an active area of study.

**Preclinical rationale for combining TALIMOGENE LAHERPAREPVEC with radiotherapy.** As previously reviewed, there is an abundance of preclinical literature to suggest that combining oncolytic immunotherapy (such as TALIMOGENE LAHERPAREPVEC) with radiotherapy can increase the antineoplastic effects of each treatment modality (Touchefeu Y Rad Onc 2011, Advani S IJROBP 2006). Irradiation of cancer cells can increase viral uptake, replication, gene expression and the induction of host cell death, thereby enhancing the effects of oncolytic immunotherapy (see Figure 1). Conversely, viral proteins can inhibit components of the DNA damage response pathway, thereby sensitizing cancer cells to the effects of radiation therapy (see Figure 2).

**Clinical experience combining TALIMOGENE LAHERPAREPVEC and radiotherapy.** Several studies have investigated the combination of oncolytic immunotherapy (such as TALIMOGENE LAHERPAREPVEC) and radiotherapy. Most relevant to the current protocol is a phase I/II trial of Talimogene Laherparepvec (formerly OncoVEXGM-CSF) and chemoradiation therapy that was reported in 2010 (Harrington KJ Clin Cancer Res 2010). Seventeen patients with locally advanced mucosal squamous cell carcinoma of the head and neck (mSCCHN) underwent high dose radiotherapy (70 Gy in 35 fractions), with concomitant cisplatin chemotherapy (100 mg/m^2) and escalating doses (10^6 – 10^8 plaque forming units (pfu)/mL) of intralesional Talimogene Laherparepvec during radiotherapy (day 1, 22, 43 and 64, see Figure 3). Escalating doses of Talimogene Laherparepvec were delivered without observation of dose limiting toxicities. Adverse events (AEs) were consistent with those normally observed during standard chemoradiation therapy for locally advanced mSCCHN), and grade 3 or 4 observed in ≥2 patients were unrelated to Talimogene Laherparepvec dose. The recommended dose of Talimogene Laherparepvec for concomitant administration with radiotherapy in future studies of mSCCHN was 10^6 followed by 10^8. This dosing schedule is consistent with previous and ongoing studies in melanoma, and other diseases (Figure 3).

The efficacy of this combination was promising. At a median follow-up of 29 months, 100% of patients achieved locoregional disease control, and 76.5% of patients were relapse-free. Notably, no patient participating in this study had measurable metastases that were not irradiated or injected with Talimogene Laherparepvec (Harrington KJ Clin Cancer Res 2010). Therefore, the systemic efficacy of this therapeutic combination was not assessed.

**Combining immunotherapy and radiotherapy.** We have previously reviewed and reported on the combinations of radiotherapy and immunotherapy (Barker and Postow IJROBP 2014). Of particular interest is the ability of the radiotherapy to augment the systemic response to immunotherapy. Evidence of this phenomenon is demonstrated by the abscopal effect, or regression of a non-irradiated tumor after radiotherapy. Investigators have previously found that the combination of granulocyte-monocyte colony stimulating factor (GM-CSF) and radiotherapy can produce an abscopal effect in 27% of patients. In the OPTiM trial described above, patients treated with GM-CSF demonstrated a non-injected visceral response rate of <5%, while those treated with Talimogene Laherparepvec demonstrated a non-injected visceral metastasis response rate of 15.2%. Whether radiotherapy combined with Talimogene Laherparepvec can increase the response rate among non-injected visceral metastases is unknown. Given that systemic response of visceral metastases that have not been injected or irradiated is a sign of successful immunotherapy, it is this endpoint that is of considerable interest for investigation.

To our knowledge, a study of Talimogene Laherparepvec and radiotherapy to characterize the systemic efficacy of this therapeutic combination has never been performed, and has not been initiated elsewhere. The present study will provide information for society regarding the potential benefit of this therapeutic combination. For patients with cutaneous metastases from melanoma, Merkel cell carcinoma, or other solid tumor malignancy this study may provide valuable therapeutic benefit from treatment using 2 active agents.

